2.4.4.5 Analyses of electrocardiogram variables

The summary statistics of all ECG variables (laboratory values and changes from baseline) will be calculated for each visit or study assessment (baseline, each post-baseline time point) by study cohort and treatment group.

A listing of ECG measurements will be provided.

The incidence of PCSAs (list provided in [Appendix B](#)) based on worst value at any time during the treatment-emergent adverse event period will be summarized by treatment groups.

The PCSA analyses will be conducted for both PAP and ETP separately. Similar analyses will be conducted for the overall avalglucosidase alfa treatment period.

2.4.4.6 Analyses of physical examinations

All physical examination variables will be listed by visits and summarized descriptive by study cohort and treatment group, as well as by dose levels among avalglucosidase alfa treated patients.

2.4.4.7 Analyses of immunogenicity parameters

Percentage of patients who seroconverted to avalglucosidase alfa and time to seroconversion will be summarized using summary statistics, by study cohort and treatment group, as well as by dose levels among avalglucosidase alfa treated patients for the overall avalglucosidase alfa treatment period.

Anti-avalglucosidase alfa and anti-alglucosidase alfa antibody titer values will be summarized using summary statistics at each study visit by study cohort and treatment group, as well as by dose levels among avalglucosidase alfa treated patients for the overall avalglucosidase alfa treatment period. Median and quartiles Q1 and Q3 titer values will be reported. All data will be presented in listings for each patient.

By patient listings will also display results of NAb, as well as results testing for IARs if clinically indicated (i.e., circulating immune complex, anti-avalglucosidase alfa IgE antibody, serum tryptase activity, complement activation, and skin testing). Descriptive summaries may also be provided as appropriate.

The following incidence rates will be summarized descriptively for each treatment group:

- ADA prevalence rate, defined as
$$100 \times (\text{number of patients with treatment-induced ADA} + \text{pre-existing ADA}) / (\text{number of evaluable patients})$$
- ADA incidence rate, defined as
$$100 \times (\text{number of patients with treatment-boosted + treatment-induced ADA}) / (\text{number of evaluable patients});$$
- Treatment induced ADA incidence rate, defined as,
$$100 \times (\text{number of patients with treatment induced ADA}) / (\text{number of evaluable patients with ADA negative at baseline});$$
- Treatment boosted ADA incidence rate, defined as
$$100 \times (\text{number of patients with treatment boosted ADA}) / (\text{number of evaluable patients with ADA positive at baseline});$$
- Incidence rate of NAbs (for inhibition of uptake, inhibition of activity and both, respectively), defined as
$$100 \times (\text{number of patients positive for NAbs}) / (\text{number of evaluable patients})$$

The kinetics of the immune responses will be analyzed as follow:

- Onset time of ADA will be analyzed descriptively using summary statistics including median and quartiles Q1 and Q3.
- Duration of ADA will be analyzed descriptively using summary statistics including median and quartiles Q1 and Q3. It will only be calculated for the patients with at least two ADA positive samples.
- The n and % of persistent ADA response will be summarized descriptively. This will be performed for the patients with at least two post baseline samples which are separated by at least 16 weeks.
- The n and % of transient ADA response will be summarized descriptively. This will be performed for the patients with at least two post baseline samples where the last sampling time point is negative.
- The n and % of indeterminate ADA response will be summarized descriptively. This will be performed for the patients with at least one post baseline sample.

ADA peak titer, last titer, and geometric mean titer will be summarized. Graphs of ADA titer over time and boxplots of the highest post-baseline ADA titer will be provided. The analyses will be performed for PAP, ETP and the overall avalglucosidase alfa treatment periods.

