- Retrospective chart review to collect available assessments prior to study entry documenting clinical decline or sub-optimal clinical response as outlined in [I 06](#) and [I 07](#) (refer to [Section 7.1](#));
- Physical examination (inclusive of Tanner stage);

- Body weight;
- Height/body length;
- Head circumference;
- Lab:
 - Serum β -HCG pregnancy test (females of childbearing potential only);
 - Safety sampling:
 - Hematology, biochemistry (including BNP and CK), and urinalysis;
 - Anti-drug antibodies (with neutralizing antibodies in ADA-positive patients) for anti-avalglucosidase alfa and anti-alglucosidase alfa antibodies;
 - Biomarkers:
 - Urine Hex4 sample collection;
 - [REDACTED]
 - [REDACTED]
 - [REDACTED]
 - GAA mutation analysis (if historical results are not available; may be obtained at any other visit if not possible during screening due to blood volume limitation)
 - Stored DNA sample (optional; may be obtained at any other visit if not possible during screening due to blood volume limitation);
 - Blood samples will be obtained as blood volume permits and will not exceed the blood volume collection limit of < 7 mL/kg over an 8-week period. Sampling is prioritized for safety labs (hematology, biochemistry, ADA) and PK and [REDACTED].
 - Muscle biopsy (optional);
 - Ventilator use diary;
 - PFT (in patients who can reliably undergo testing and/or who are not invasively ventilated);
 - 6MWT (in patients who are able to ambulate at least 40 meters [approximately 130 feet] without stopping and without an assistive device);
 - GMFM-88/GMFCS-E&R
 - Motor Skills Checklist;
 - QMFT;
 - Pompe-PEDI, Functional Skills Scale: Mobility Domain;
 - Bayley-III/Leiter-3 scales;
 - Echocardiography;
 - Hearing testing;
 - Eyelid position measurements;

- PedsQL Generic Core Scale questionnaire (≥ 24 months of age);
- PedsQL Pediatric Pain Questionnaire (> 5 years of age);
- Pain VAS;
- AE collection;
- Prior/concomitant medications/therapies;
- IRT contact for notification of screening.

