1.6 STATISTICAL MODIFICATIONS MADE IN THE STATISTICAL ANALYSIS PLAN

The listing below gives the rationale and key details of major changes to Statistical Analysis Plan Version 1.0.

- In retrospective Chart Review, update “new onset of ptosis” to “presence of ptosis”.
- Update part of the definition of transient ADA response from “treatment induced ADA detected at two or more sampling time points during the treatment, where the first and last ADA-positive samples are separated by a period less than 16 weeks, and the patient’s last sample time point is ADA-negative” to “the last sample time point is positive and separated by <16 weeks from the first positive result”.
- Treatment-boosted ADAs are excluded from the analysis of ADA kinetics. If many patients have preexisting ADAs, kinetics of boosting will be described separately.
- The assessment of NAb response is simplified.

- Expand the composite score from cohort 3 to all population in [Table 1](#)
- Update the wording on re-randomization test for efficacy endpoints besides to composite score
- Update PCSA following ISS

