Treatment-boosted ADAs are excluded from the analysis of ADA kinetics. If many patients have preexisting ADAs, kinetics of boosting will be described separately.

For the assessment of NAb response, the qualitative sample status will be assessed and be categorized into the following classes:

- NAb-negative sample: a sample is considered negative if NAb are not detected.
- NAb-positive sample: sample in which NAb is detected.

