2.4.6 Association of ADA with safety

Selected safety parameters (AEs, SAEs, IARs and potential immune complex mediated reactions) will be summarized by ADA and NAb response categories.

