2.4.8.2 Subgroup analyses

Due to the limited power in these subpopulations, selected subgroup analyses, if appropriate, may be explored using descriptive statistics or graphically by treatment group for the overall avalglucosidase alfa treatment period only.

The following baseline factors may be explored to assess their impact on efficacy with exploratory analysis: prior alglucosidase treatment duration, duration of disease, age at first alglucosidase infusion, age at first infusion of avalglucosidase alfa, gender, race, ethnicity, baseline status on invasive ventilatory support, baseline use of noninvasive ventilatory support, baseline status on assistive device use, baseline LVM Z-score, baseline GMFCS level, GAA genotyping, CRIM status, [REDACTED], quartiles of peak IgG antibody titer and status of inhibitory antibody.

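### The neutralizing antibody incidence rate has no baseline condition, so antibodies present before the first avalglucosidase alfa dose count as incident

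*SAP*

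**What the plan says.** SAP 2.4.4.7 lists several rates to be given for each treatment group. The NAb entry is headed "Incidence rate of NAbs (for inhibition of uptake, inhibition of activity and both, respectively), defined as" and its numerator is the "number of patients positive for NAbs"; the denominator is all evaluable patients. The ADA entries beside it are conditioned on baseline. Treatment-induced ADA is divided by the "number of evaluable patients with ADA negative at baseline", treatment-boosted ADA by those positive at baseline, and prevalence has its own line.

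SAP 2.1.3.8 sorts ADA into pre-existing, treatment-induced and treatment-boosted. For NAb it gives only a sample-level class: "NAb-positive sample: sample in which NAb is detected". SAP 1.6 records that "The assessment of NAb response is simplified".

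The baseline data are planned. Protocol 10.1.1 lists at screening: "Anti-drug antibodies (with neutralizing antibodies in ADA-positive patients) for anti-avalglucosidase alfa and anti-alglucosidase alfa antibodies".

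Two related places:
- SAP 2.4.8.2 includes, among factors it calls baseline, "quartiles of peak IgG antibody titer and status of inhibitory antibody".
- SAP 2.4.6 is one sentence: "Selected safety parameters (AEs, SAEs, IARs and potential immune complex mediated reactions) will be summarized by ADA and NAb response categories".

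**The concern.** An incidence rate should count new cases among patients who could become cases. This ratio is closer to a period prevalence. The difference matters here for three reasons:

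- Inclusion criterion I 05 requires at least 6 months on a stable dose of alglucosidase alfa, and Protocol section 4 describes avalglucosidase alfa as that enzyme with added glycan. Antibodies raised by the earlier product may react with the new one.
- Eligibility does not remove such children. E 01 excludes titres of 1:25600 or more at two consecutive time points. E 05 adds IgE antibodies and, on the investigator's judgement, a history of high sustained IgG. A child with a lower titre and NAbs can enter.
- SAP 2.1.3.8 itself provides for the case that many patients have pre-existing ADA.

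Immunogenicity is part of the primary safety endpoint. A NAb incidence shown for an avalglucosidase alfa group will be read as the drug's own neutralizing response, although part or all of it may predate the drug.

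**Working it through.** The documents state no NAb rate, so there is no figure to reproduce. The check compares the two definitions.

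**Inputs**
- N = evaluable patients. SAP 2.3.3 requires a reportable post-baseline ADA sample and does not exclude patients positive at baseline.
- N = 15 is the minimum planned number on avalglucosidase alfa in the 25-week primary analysis period: 5 in Cohort 1, 5 in Cohort 2, and 5 of the 10 in Cohort 3 under 1:1 allocation. N = 5 represents a single cohort or arm.
- b = patients NAb-positive at baseline and i = patients newly NAb-positive. Both are **assumed**.

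**Formulas**
- As the SAP defines it: 100 × (b + i) / N
- Treatment-emergent: 100 × i / (N − b)
- Difference: 100 × b × (N − b − i) / [N × (N − b)]

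The difference is zero only if b = 0 or if every patient is positive (b + i = N). Otherwise the SAP rate is the higher one.

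| N | b | i | SAP definition | Treatment-emergent |
|---|---|---|---|---|
| 15 | 0 | 1 | 1/15 = 6.7% | 1/15 = 6.7% |
| 15 | 3 | 0 | 3/15 = 20.0% | 0/12 = 0% |
| 15 | 3 | 1 | 4/15 = 26.7% | 1/12 = 8.3% |
| 15 | 5 | 1 | 6/15 = 40.0% | 1/10 = 10.0% |
| 5 | 1 | 0 | 1/5 = 20.0% | 0/4 = 0% |
| 5 | 2 | 1 | 3/5 = 60.0% | 1/3 = 33.3% |

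Reading the numerator as post-baseline positivity only would not cure this. A child positive at baseline and still positive afterwards is counted all the same.

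**Subgroup factor.** SAP 2.4.4.7 plots the highest post-baseline ADA titre, and nothing defines a baseline peak. A peak titre is therefore a value reached on treatment and does not belong in a list of baseline factors. For inhibitory antibody status no time point is given.

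**The case against.** The strongest defence is that the formula is explicit and the output descriptive. SAP 2.4.4 plans no inferential safety testing, SAP 2.4.8.1 calls the study non-confirmatory, and NAb results are listed by patient, so in about 20 children baseline positivity can be seen. The list is introduced as incidence rates yet contains a prevalence line, so the word is used loosely. This stands as a limit on severity. It does not remove the defect: the summary rate is what gets quoted, and the ADA lines show that the SAP separates the concepts when it intends to.

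The alglucosidase alfa arm is a weak corrective. It exists only in Cohort 3. Protocol 9.1.1.7 samples it for anti-avalglucosidase alfa ADA only at baseline and Week 25, and SAP 2.1.3.8 says only anti-alglucosidase alfa ADA is evaluated there.

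A fair objection to any remedy is that NAb is tested only in ADA-positive samples, so a baseline-negative denominator needs a rule for untested patients. That stands and is met in the fix.

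Stronger readings that a reader might infer, but that the documents do not support:
- *The ADA-safety table counts events before seroconversion as effects of avalglucosidase alfa.* SAP 2.4.6 gives no event-counting rule and does not define its categories; the induced and boosted classes of SAP 2.1.3.8 could be meant. In avalglucosidase alfa patients these events are treatment-emergent under any antibody split (SAP 2.1.3.1). At most they would sit in the wrong antibody column. This is an omission, not a stated wrong rule.
- *Longer follow-up alone will make antibody-positive patients look worse.* The primary analysis period is a planned 25 weeks for everyone, so apart from dropout this could arise only in extension or pooled data.
- *ADA incidence has the same flaw.* It separates pre-existing from induced and boosted ADA. The remaining gap is that a missing baseline ADA sample is taken as negative.

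**Conclusion.** The NAb incidence rate is wrong as defined: it counts pre-existing NAb as incident in a fully pretreated population. The size depends on baseline NAb frequency, which the documents do not give. With an assumed 3 of 15 positive at baseline and none converting, the overstatement is 20 percentage points; with nobody positive at baseline it is nil. The error affects a descriptive output of the primary safety endpoint and no hypothesis test, so it should be corrected but does not threaten the trial's conduct.

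Listing peak IgG titre as a baseline factor is also wrong, but it touches only optional exploratory subgroups. For inhibitory antibody status and for the categories in SAP 2.4.6, the finding is only that timing and definitions are not stated.

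**What to change.** **SAP 2.4.4.7**
1. Report baseline NAb prevalence as its own line.
2. Define treatment-emergent NAb incidence, for uptake, activity and both, as NAb-negative at baseline and positive after the first avalglucosidase alfa dose, over evaluable patients NAb-negative at baseline.
3. Class baseline ADA-negative patients as NAb-negative, and state the rule for a missing baseline NAb.
4. For Cohort 3 patients who switch, use the last sample before the first avalglucosidase alfa dose as baseline. Protocol 9.1.1.7 and 10.1.2.6 plan an anti-avalglucosidase alfa sample at Week 25. SAP 2.1.3.8 should be aligned with them so that this baseline is available.

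**SAP 2.4.8.2.** Replace peak IgG titre with baseline titre, or move it out of the baseline list. State that inhibitory antibody status is the baseline value.

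**SAP 2.4.6 (clarification).** Define the response categories, show pre-existing positives as their own group, and split events at the first positive sample.

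**Cost.** SAP wording and programming; the samples are already in the protocol. Denominators become smaller (15 to 12 in the main illustration, 5 to 3 in the last table row), so counts should be shown beside percentages.

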The ADA titer of the positive samples will also be assessed. A titer represents quasi-quantitative information on the level of ADA present in a sample. Confirmed positive samples are serially diluted until a negative result is achieved. The titer is subsequently defined as the reciprocal of the last dilution that tests positive. The minimal required dilution (MRD) will be incorporated in the final calculation.

The ADA attributes will be determined by the following conditions:

- Pre-existing ADAs: antibodies reactive with the study drug present in patient at the baseline assessment.
- Treatment induced ADAs: ADAs developed de novo (seroconversion) following administration of the study drug. If the baseline ADA sample is missing or non-reportable and at least one reportable on-treatment ADA sample is available, the baseline sample will be considered as “negative”.
- Treatment boosted ADAs: Pre-existing ADAs that were boosted at least two titer steps from baseline (i.e., 4 fold increase in titers) following administration of the study drug (any time after the first drug administration).

The following kinetics of the ADAs will be analyzed:

- Onset of ADA is defined as the time period (in days) between the first study drug administration and the first instance of treatment induced ADAs.
- Duration of ADA will be calculated as the date of last treatment induced ADA sample minus the date of first treatment induced or boosted ADA sample + 1.
- Persistent ADA response is defined as,
 - Treatment induced ADAs detected at two or more sample time points during the treatment, where the first and last ADA-positive on-treatment sample (irrespective of any negative samples in between) are separated by at least 16 weeks.

- Transient ADA response is defined as,
 - Treatment induced ADA detected only at one sampling time point during the treatment, followed by an ADA-negative value; Or,
 - Treatment induced ADA detected at two or more sampling time points during the treatment, where the first and last ADA-positive samples are separated by a period less than 16 weeks, and the patient's last sample time point is ADA-negative.
- Indeterminate ADA response is defined as,
 - Only the last sample time point is positive; Or
 - The last sample time point is positive and separated by <16 weeks from the first positive result.

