2.3.3 Additional analysis populations

The ETP population will consist of safety patients who receive at least one avalglucosidase alfa dose during ETP.

The PK population will consist of patients from the safety population in PAP who have evaluable drug concentration data. PK analysis for cohort 3 patients who switch to avalglucosidase alfa during the ETP will be reported in the final CSR.

For Cohort 1 and Cohort 2, the PD or pharmacogenetic analysis population for the parameter of interest will consist of safety patients who have evaluable PD or pharmacogenetic data for the parameter of interest. For cohort 3, the PD or pharmacogenetic analysis population for the parameter of interest will consist of mITT patients who have evaluable PD or pharmacogenetic data for the parameter of interest.

The ADA evaluable population will consist of patients from safety population who have at least one ADA sample taken post-baseline after drug administration that is appropriate for ADA testing with a reportable result. Patients with missing or non-reportable baseline samples and reportable post-baseline samples will be considered as evaluable.

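### The transient ADA percentage is taken only among patients whose last sample is negative, which can only raise it and makes it non-comparable with the persistent and indeterminate percentages

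*SAP*

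**What the plan says.** SAP section 2.1.3.8 (Immunogenicity) defines three classes of treatment-induced ADA response.

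- **Persistent:** the first and last positive on-treatment samples, "irrespective of any negative samples in between) are separated by at least 16 weeks". There is no condition on the last sample.
- **Transient:** either "Treatment induced ADA detected only at one sampling time point during the treatment, followed by an ADA-negative value", or two or more positives less than 16 weeks apart where the patient's "last sample time point is ADA-negative".
- **Indeterminate:** only the last sample is positive, or "The last sample time point is positive and separated by <16 weeks from the first positive result".

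The same section excludes treatment-boosted ADA from the kinetics.

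SAP section 2.4.4.7 then asks for n and % of each class and attaches a patient set to each.

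- **Persistent:** "This will be performed for the patients with at least two post baseline samples which are separated by at least 16 weeks".
- **Transient:** "This will be performed for the patients with at least two post baseline samples where the last sampling time point is negative".
- **Indeterminate:** "This will be performed for the patients with at least one post baseline sample".

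SAP section 2.3.3 defines the ADA evaluable population by "at least one ADA sample taken post-baseline after drug administration that is appropriate for ADA testing with a reportable result", which is essentially the indeterminate set.

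**The concern.** The persistent and indeterminate sets depend only on which samples were taken. The transient set also depends on a test result, and that result is part of the transient definition. Patients who belong to another class because they end positive are taken out of the transient base, while the transient numerator stays whole.

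Immunogenicity is part of the primary safety endpoint (Protocol, Clinical Trial Summary), and SAP section 2.4 displays summaries by cohort and arm, planned at about five patients each. With so few patients, a base that shrinks according to the result can turn one patient into a large percentage. A reader who sets the three percentages next to each other, or adds them, will be misled about how treatment-induced responses divide.

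**Working it through.** The documents give no figure to reproduce, so the check is on the logic, followed by assumed examples.

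**Step 1: do the classes partition treatment-induced patients?** Take any patient with at least one treatment-induced positive.
- Two or more positives, first and last at least 16 weeks apart: persistent.
- Otherwise, last sample negative: transient.
- Otherwise, last sample positive: indeterminate.

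The classes are exclusive and exhaustive. The first transient limb also implies a negative last sample, because the only positive is followed by a negative.

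**Step 2: what does the filter remove?** Use the anti-avalglucosidase schedule in the primary analysis period (Protocol sections 9.1.1.7 and 10.1.2.5): Day 8 and Weeks 5, 9, 13, 17, 21, 25, or nominal days 8, 29, 57, 85, 113, 141, 169. Seven samples give 2^7 = 128 positive/negative patterns. Sixteen weeks is 112 days. If the first and last positives are samples *i* and *j*, the samples between them are free, giving 2^(j−i−1) patterns.

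- Persistent, last positive at Week 21 (ends negative): Day 8 to Week 21 gives 16; Week 5 to Week 21 gives 8. Total 24.
- Persistent, last positive at Week 25 (ends positive): from Day 8, 32; from Week 5, 16; from Week 9, 8. Total 56.
- Indeterminate: first positive at Week 13, 17 or 21 and last at Week 25 gives 4 + 2 + 1 = 7; only Week 25 positive gives 1. Total 8.
- Never positive: 1.
- Transient: 128 − 80 − 8 − 1 = 39, all ending negative.

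The last-negative filter removes 0 of 39 transient, 8 of 8 indeterminate and 56 of 80 persistent patterns. It keeps the never-positive pattern. These are counts of patterns, not of expected patients.

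A fully sampled patient has samples more than 16 weeks apart (Day 8 to Week 21 is 19 weeks), so for such patients the persistent and indeterminate sets are the same people.

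**Step 3: direction.** Let T be the number of transient patients, N never positive, P− and P+ persistent ending negative and positive, and I indeterminate, all with at least two post-baseline samples and negative at baseline.

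- SAP transient % = T / (T + N + P−)
- Among all with two or more samples = T / (T + N + P− + P+ + I)

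The numerator is the same and the first denominator is never larger, so the SAP figure is equal or higher. The ratio of the two is 1 + (P+ + I) / (T + N + P−).

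**Step 4: size.** The mixes are assumed: 16 fully sampled patients, all ADA-negative at baseline, T = 2 throughout.

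| N | P+ | P− | I | Transient, SAP | Transient, all 16 | Transient, treatment-induced | Persistent, SAP | Indeterminate, SAP | Sum of SAP % | Sum on all 16 |
|---|---|---|---|---|---|---|---|---|---|---|
| 10 | 2 | 0 | 2 | 2/12 = 16.7% | 12.5% | 2/6 = 33.3% | 12.5% | 12.5% | 41.7% | 6/16 = 37.5% |
| 4 | 6 | 0 | 4 | 2/6 = 33.3% | 12.5% | 2/12 = 16.7% | 37.5% | 25.0% | 95.8% | 12/16 = 75.0% |
| 2 | 8 | 1 | 3 | 2/5 = 40.0% | 12.5% | 2/14 = 14.3% | 56.25% | 18.75% | 115.0% | 14/16 = 87.5% |
| 0 | 10 | 0 | 4 | 2/2 = 100% | 12.5% | 2/16 = 12.5% | 62.5% | 25.0% | 187.5% | 16/16 = 100% |

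In a group of five with one transient patient and four ending positive, the SAP rule reports 1/1 = 100%, against 1/5 = 20%.

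For the second row, the proposed base gives 2/12 = 16.7%, 6/12 = 50.0% and 4/12 = 33.3%, which sum to 100%.

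**The case against.** The strongest defence is that SAP section 2.4.4.7 never calls these sets denominators. Where it fixes a base for an ADA rate, as for prevalence, incidence, induced and boosted ADA and neutralizing antibodies, it writes a ratio. SAP section 2.4 has a default that ties percentages to the analysis population used, and section 2.3.3 supplies an ADA evaluable population. On that view, the three sentences only say who can be classified.

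It stands that the wording is not explicit. The default does not rescue the plan, however: it points to the population used, and these sentences name that population for each class. As a rule for who can be classified, the transient sentence would still be odd, since a patient ending positive is fully classifiable as not transient.

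A second objection is that a base of all treatment-induced patients loses the 16-week follow-up condition. The classes still cover such patients: one with short follow-up is indeterminate if ending positive and transient if ending negative. Short follow-up can lower the persistent share, which is why a count of patients without samples 16 or more weeks apart should accompany the table.

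Three stronger readings are tempting and not supported.

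- **The percentage is conditioned on its whole outcome.** The filter uses one necessary component. Never-positive patients and persistent patients ending negative remain in the base, so 100% is a limiting case.
- **There are three different denominators in practice.** For fully sampled patients in the primary analysis period, two of them coincide and only the transient set stands apart.
- **The filter can also dilute the percentage.** Against all patients with two or more samples it cannot. The figure falls below the treatment-induced share only when many patients are never positive, as in the first row of the table. That, like any shift in the persistent and indeterminate percentages on moving to the treatment-induced base, reflects the choice of base rather than this filter.

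**Conclusion.** The point holds for the transient percentage. Its base is selected on a negative last sample, so it equals or exceeds the value among all patients with at least two post-baseline samples, and it cannot be compared with or added to the other two. With 2 transient patients of 16 held fixed, the reported figure ranged from 16.7% to 100% against 12.5%.

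This rests on reading each named set as the denominator of its percentage, on nominal sampling days with complete sampling, and on assumed patient mixes in which everyone is ADA-negative at baseline. The direction does not depend on the mix; the size does.

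The matter is minor. A reader might infer that the primary safety conclusion is affected, but the documents do not support that. SAP section 2.4.4 makes safety analyses essentially descriptive with no inferential testing. Counts are shown beside percentages, and section 2.4.4.7 lists all antibody data by patient. Class membership, and hence any use of these classes in the safety summaries by ADA category in section 2.4.6, is unchanged.

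**What to change.** In SAP section 2.4.4.7:

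1. Delete the requirement that the last sample be negative from the transient summary.
2. Report persistent, transient and indeterminate response on one base, patients with treatment-induced ADA, so that the three percentages sum to 100%.
3. Optionally add a second column on ADA-evaluable patients who were ADA-negative at baseline. The three percentages then add up to the treatment-induced incidence rate already defined in that section.
4. State the number of patients who lack post-baseline samples 16 or more weeks apart, since they cannot be classed as persistent.

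The cost is a few lines of SAP wording and the matching table shell. No new data, visits or samples are needed.
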